Survey/Questionnaire research

Observational research

Prospective Clinical Research

Power Analysis

Size of study groups: 100 total participants.

Procedures:

All visits are standard of care, however completion of questionnaires will be for study purposes in follow-up clinic visits and at specified time-frames. Study involvement includes the following visits:

Screening: Questionnaires and clinical examination

Enrollment: Questionnaire and clinical examination

Follow-up:

- 1 month post-injection- questionnaires and clinical exam
- 2 months post-injection- questionnaire and clinical exam
- 3 months post-injection- questionnaire and clinical exam
- 6 months post-injection- questionnaire and clinical exam
- 9 months post-injection- questionnaire and clinical exam
- 12 months post-injection- questionnaire and clinical exam
- 24 months post-injection- questionnaire and clinical exam
- 36 months post-injection- questionnaire and clinical exam

Questionnaires: Demographics, medication use (MSQ III), ODI, PROMIS PF CAT, PROMIS Global 10, NRS for back and leg pain (current, average last week), PGIC score, PSQ-3, and patient satisfaction with treatment score (5 point: 1, very dissatisfied; 2, dissatisfied; 3, neither satisfied nor dissatisfied; 4, satisfied; and 5, very satisfied).

Data Collection:

An electronic data collection sheet (via iPad) will be used to record all pre-procedure data (see data collection sheet):

- 1) Age (years).
- 2) Sex.
- 3) Height (cm).
- 4) Weight (Kg).
- 5) Duration of pain (weeks).

6) Radiologic diagnosis based on MRI of the Lumbar Spine.
7) NRS for pain; separate scores for back pain and for leg pain

- 8) Oswestry Disability Index (ODI)
- 9) PROMIS Physical Function scale version 2
- 10) PROMIS Global 10
- 11) Medication Quantification Scale (MQS III) score
- 12) Daily opioid use in morphine equivalents

Additional questions for post procedure survey

- 13) Patient Global Impression of Change (PGIC)
- 14) Patient satisfaction score (five-point Likert scale: 1, very dissatisfied; 2, dissatisfied; 3, neither satisfied nor dissatisfied; 4, satisfied; and 5, very satisfied)

Immediately after injection the following will be obtained:

- 15) Fluoroscopy time
- 16) Post-injection NRS pain score; separate scores for back pain and for leg pain
- 17) Adverse events, if they occurred

Data Storage:

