Hard copy data will be collected and stored in a password-protected computer located in the Division of PM&R. Participants will each be assigned an ID number that will be used as the sole identifier on any documents. Participant data will be compiled onto a single password protected file, where they will only be identified by their ID number. An enrollment log will be the only file where subject names are correlated with ID numbers. This will be kept in a separate, secure, password-protected file in the Division of PM&R.

Data Analysis Plan

The primary outcome will be the proportion of participants with >80% and >50% reduction in back pain on the NRS pain score at the 2-month follow-up assessment. Secondary outcomes included reduction in median NRS pain score, ODI, change in PROMIS PF-CAT, MQS III, opioid consumption in daily morphine equivalents, PGIC score, PSQ-3, and satisfaction score. Secondary outcomes will also be defined based on categorical “responder analysis” definitions of important clinical change given the National Institutes of Health recommendation for responder analysis in the assessment of therapeutic spine pain interventions. The responder analysis will include the proportion of patients with 30% or greater improvement on the ODI, a PGIC score less than 3 (indicating “improved” or “very much improved”), a 6.8 or greater point reduction on the MQS III score (equivalent to approximately 10 daily morphine equivalents), and the proportion of participants who undergo surgical spine surgery in the study period.

Statistical analysis

Means and standard deviations of subject demographic data, as well as pain, functional, and treatment satisfaction scores will be calculated. Intergroup differences will be assessed by t test for numerical data and Chi Square or Fisher Exact test for categorical data. Regression modeling will be implemented using ANOVA to assess for patient traits and characteristics that increase the likelihood of efficacy using one technique as opposed to the other.

Risks/Benefits:

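### The predictor analysis names ANOVA for an undefined likelihood of efficacy and asks for a contrast between two techniques when only one is described

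*Combined protocol and SAP*

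**What the plan says.** The Data Analysis Plan section states: "The primary outcome will be the proportion of participants with >80% and >50% reduction in back pain on the NRS pain score", assessed at 2 months. Both thresholds give a yes/no result for each participant. The section adds further yes/no outcomes: "The responder analysis will include the proportion of patients with 30% or greater improvement on the ODI, a PGIC score less than 3", a reduction of at least 6.8 points on the MQS III, and spine surgery. It also lists numerical or ordinal outcomes: "Secondary outcomes included reduction in median NRS pain score, ODI, change in PROMIS PF-CAT, MQS III, opioid consumption in daily morphine equivalents", among others.

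The Statistical analysis section then gives the methods. Group comparisons are covered by one sentence: "Intergroup differences will be assessed by t test for numerical data and Chi Square or Fisher Exact test for categorical data". The search for predictors is covered by another: "Regression modeling will be implemented using ANOVA to assess for patient traits and characteristics that increase the likelihood of efficacy". That sentence ends by asking about the "likelihood of efficacy using one technique as opposed to the other".

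The Power Analysis section gives only "Size of study groups: 100 total participants", with no response rate, effect size, significance level or dropout. The documents contain no logistic or other binary-outcome regression, no list of predictors and no second technique.

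**The concern.** Two things in the predictor sentence do not fit the rest of the plan.

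- **The contrast.** The objectives, procedures and risks describe a single intervention, an intradiscal PRP injection. With no second technique there are no data from which to learn who does better with one than with the other.
- **The model.** The question is about a probability of success and the primary outcome is a proportion of responders, but the method named is one for the mean of a continuous outcome. Most of the traits on the data collection sheet are numeric (age, height, weight, pain duration, NRS, ODI, PROMIS scores, MQS III, opioid dose). A linear fit of a 0/1 response on such traits can leave the range 0 to 1, and it assumes a constant variance that a binary outcome does not have.

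At stake is whether the predictor analysis can be carried out as written, and whether response probabilities reported from it can be trusted. Because the outcome, threshold, visit and predictors are all left open, they could be chosen after the data are seen.

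**Working it through.** **Inputs.** From the documents: 100 participants, a binary primary outcome at two thresholds, and 12 pre-procedure items on the data collection sheet. The plan gives no figure to reproduce here. Response rates, odds ratios and a single normally distributed trait are assumptions.

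**1. What ANOVA does with a 0/1 response.** Take two trait groups with 15/50 and 25/50 responders.
- Linear model: difference = 0.50 − 0.30 = 0.20, F-test p = 0.0416.
- Pearson chi-square: p = 0.0412.
- Logistic regression: odds ratio = (25/25)/(15/35) = 2.33, likelihood-ratio p = 0.0404.

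The three tests agree, and the linear model returns the risk difference exactly.

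**2. Tests of a continuous trait at N = 100** (1,000 simulated trials per setting; response at the trait mean 20%, 30% or 50%).
- No effect: rejection in 4.8–5.5% (linear) and 4.9–5.9% (logistic).
- Odds ratio 2 per SD: power of about 77%, 87% and 90%, with the two methods within 1 point of each other.

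In separate runs at response rates of 15–50%, the 95% interval for the linear slope covered 92–98%.

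**3. Fitted probabilities and their intervals, 20% overall response.** The best straight line passes through 0.20 at the trait mean with slope b, the average of x·p(x) over the trait distribution. The share of negative fitted values in a large sample is Φ(−0.20/b). The line at 1.5 SD is 0.20 + 1.5b. Coverage is for the true response probability at 1.5 SD, from 20,000 simulated trials of 100.

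| Odds ratio per SD | b | −0.20/b | Negative fitted values | Line at 1.5 SD | True probability | Coverage of nominal 95% interval |
|---|---|---|---|---|---|---|
| 1.5 | 0.0632 | −3.16 | 0.1% | 0.29 | 0.30 | 92% |
| 2 | 0.1030 | −1.94 | 2.6% | 0.35 | 0.38 | 88% |
| 3 | 0.1484 | −1.35 | 8.9% | 0.42 | 0.49 | 79% |

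In samples of 100 the slope is itself uncertain, and the average negative share is a little higher: 1.2%, 3.8% and 9.1%. At least one impossible fitted value appears in roughly 70% of trials at an odds ratio of 2 and 97% at 3.

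Coverage falls for two reasons. At an odds ratio of 3 the pooled residual variance is 0.20 × 0.80 − 0.1484² = 0.138, while the variance at the true probability is 0.49 × 0.51 = 0.250, so the interval is too narrow. The line is also too low there (0.42 against 0.49). At 50% response the problem disappears: coverage is about 96–97% at these odds ratios.

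**4. How many traits the data can carry.** One term for each of the 12 items gives 20/12 = 1.7, 30/12 = 2.5 or 50/12 = 4.2 responders per predictor at 20%, 30% or 50% response, before dropout. Five predictors give 20/5 = 4, 30/5 = 6 or 50/5 = 10.

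**5. The contrast.** The sentence needs a technique variable with two values. Every participant receives the same one, so a technique effect, or a trait-by-technique interaction, is not estimable by ANOVA, logistic regression or anything else.

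**The case against.** The strongest defence is that a linear model on 0/1 data is a recognised method. It estimates response probabilities and risk differences, its type I error is near nominal here, and its power matches logistic regression. Which traits are flagged would hardly change. This stands. A reader might infer that ANOVA cannot estimate a likelihood of response, or that its standard errors are invalid. Steps 1 and 2 do not support either.

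Secondly, the sentence names no dependent variable, and the plan has continuous outcomes for which linear models are conventional. This also stands: a binary reading is natural but is not stated. It leaves efficacy undefined, which is itself a reason to rewrite the sentence.

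Thirdly, the share of negative fitted values depends heavily on the assumed odds ratio, and 9% needs a very strong predictor. That is right, so the range is shown. Fitted values outside 0 to 1 also matter mostly for individual prediction, which the plan does not propose.

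Fourthly, a reader might blame ANOVA for false predictors. With 10 independent tests at 5% the chance of at least one is 1 − 0.95^10 = 40%, but logistic regression would give the same figure. The number of responders per predictor likewise limits either model. Both are separate reasons for a short list.

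Finally, the planned group tests could be read as comparing responders with non-responders, which would be workable. That reading does not rescue the technique contrast.

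**Conclusion.** The concern holds in a limited form. The technique contrast is wrong as written, and this rests on no numerical assumption: one technique is described, so nothing can be contrasted with it. The choice of ANOVA is a poor fit rather than an invalid one. If efficacy means the binary response, tests of traits are close to valid at 100 participants. What is lost is an odds ratio, fitted values confined to 0 to 1, and dependable intervals for response probability when response is uncommon. At an assumed 20% response those intervals cover about 92%, 88% and 79% at odds ratios of 1.5, 2 and 3 per SD; at 50% response they do not fall short. This bears most on the more-than-80% outcome, which must have no more responders than the more-than-50% outcome.

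A reader should not infer that the primary result is affected. The primary outcome is a simple proportion and does not depend on this model.

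**What to change.** Rewrite the predictor sentence in the Statistical analysis section:

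- Delete the closing clause that contrasts two techniques.
- Define efficacy for this analysis as more than 50% reduction in back pain NRS at 2 months.
- Replace ANOVA with logistic regression on a short fixed list of baseline variables already collected, for example NRS, age, pain duration, ODI and daily opioid use. Report odds ratios with 95% confidence intervals.
- For more than 80% reduction, use a penalised fit (such as Firth's) or fewer predictors if responders are few.
- Keep linear models for the continuous outcomes.
- Label the analysis exploratory.

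The cost is wording only: no new data, visits or participants. The one drawback is that fewer traits can be examined. The five named variables are an example; the sponsor should settle the list before looking at outcome data.

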Risks of study participation are the same as those for any standard fluoroscopically guided lumbar intradiscal injection performed in the PM&R Spine Clinic. These include: local infection, intradiscal infection (discitis), epidural hematoma or abscess, dural puncture and potential post-dural puncture headache, paresthesia during needle placement, pain at the injection site, failure to relieve pain, allergic reaction to products or medications being used. Utilizing fluoroscopy, the risk of nerve damage, spinal cord injury or intravascular injection is less than 1:500,000. The length of stay and length of recovery is no longer than that of a standard spinal injection performed in the PM&R Spine Clinic at present.

There are no direct benefits to the individual by participating in this study. The patients will be presented with the same options of treatment whether they enroll in the study or decide not to. The information extracted from this study may provide the investigators a better understanding of a patient's short and long-term pain response and physical function following a intradiscal PRP injection.

Study Termination Criteria

- Adverse events considered/identified by the medical staff during the procedure process
- The subject requests to be withdrawn from the study during the procedure.

Safety Monitoring Plan

Safety will be monitored by all members of the study team:

[name]

[name], DO

The Principal Investigator is a physician at the University of Utah Health Sciences Center. Members of the data and safety monitoring committee will be in close contact with all the subjects throughout the study, both in-person and via telephone. The members of the data and safety monitoring committee will review potential side effects and adverse reactions with each subject at the time of delivery of the study drug and at the time of each sample collection. All the committee members are located at the University of Utah Orthopaedic Center; all members have research experience.

References

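### Any adverse event during the procedure is a study termination criterion, and the plan does not say that these patients stay in follow-up or in the responder denominator

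*Combined protocol and SAP*

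**What the plan says.** The Combined protocol and SAP has a two-item section headed Study Termination Criteria. The first item is "Adverse events considered/identified by the medical staff during the procedure process". The second is "The subject requests to be withdrawn from the study during the procedure". The section does not say what termination means for later visits, for recording of adverse events or for use of the data.

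Four other places bear on the point:

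- **Data Analysis Plan:** "The primary outcome will be the proportion of participants with >80% and >50% reduction in back pain on the NRS pain score", assessed at 2 months. The secondary responder definitions are worded alike: "The responder analysis will include the proportion of patients with 30% or greater improvement on the ODI". No analysis set is defined, and there is no rule for missing scores or for terminated patients.
- **Data Collection:** "Adverse events, if they occurred" is listed among the items obtained straight after the injection. It is not listed for any later visit.
- **Procedures:** follow-up visits run from 1 to 36 months. "All visits are standard of care", but the same sentence says that the questionnaires are completed for the study.
- **Safety Monitoring Plan:** the committee "will be in close contact with all the subjects throughout the study, both in-person and via telephone". Its review of adverse reactions is tied to delivery of the study drug and to sample collection, and the visit schedule contains no sample collection.

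**The concern.** Whether a patient is terminated under the first item depends on a safety outcome, so any loss that follows is unlikely to be random. Because the item has no severity threshold, a minor and foreseeable event could meet it. Risks/Benefits lists paresthesia at needle placement and injection-site pain among the known risks.

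Two things are at stake. The later course of patients who had a procedural event may go unrecorded, including whether they come to spine surgery, which is a listed outcome. The 2-month responder proportion may also be calculated without them, and it would then be too high if they do worse than the others. Both primary thresholds (more than 50% and more than 80% pain reduction) would be affected.

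**Working it through.** **Step 1: what the criterion does.** The second item is about one subject and says that the subject leaves the study. The two items share one heading. The list therefore reads most naturally as ending an individual's participation, and not merely as stopping the injection or closing the whole study.

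**Step 2: whether another section keeps these patients in.**

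| Question | What the document gives |
|---|---|
| Is the procedural event itself recorded? | Yes, among the post-injection items |
| Do adverse event checks continue afterwards? | Contact with all subjects is promised, but review is tied to sample collections that are not scheduled; whether a terminated patient is still a subject is not stated |
| Do study questionnaires continue? | Not stated |
| Does the patient stay in the denominator? | Not stated; no analysis set or missing-data rule |

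No section settles the last two questions, and the second is settled only in part.

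**Step 3: possible size for the responder proportion.** The plan has no figure of its own to reproduce. The total of 100 under Power Analysis comes without inputs, and no procedural event rate is given. Everything below except N is therefore assumed.

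- N = 100 patients in whom the injection was started (the planned total)
- k = number terminated for a procedural event (assumed)
- p = responder rate among those retained (assumed)
- q = responder rate among those terminated (assumed)

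If the terminated patients are dropped, the reported rate is p. The rate among all injected is [(N − k)p + kq]/N. The difference is k(p − q)/N.

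Worked case: k = 5, p = 50%, q = 0 (counted as non-responders). The all-injected rate is 95 × 0.50/100 = 47.5%, against 50% of those retained. The difference is 2.5 points.

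Difference in percentage points with q = 0:

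| k | p = 30% | p = 50% | p = 60% |
|---|---|---|---|
| 1 | 0.3 | 0.5 | 0.6 |
| 2 | 0.6 | 1.0 | 1.2 |
| 5 | 1.5 | 2.5 | 3.0 |
| 10 | 3.0 | 5.0 | 6.0 |

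If q = 25% with k = 5 and p = 50%, the difference is 5 × 0.25/100 = 1.25 points. If q = p it is zero, and if q exceeds p it changes sign.

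**Step 4: scale.** The 95% half-width at n = 100 and p = 50% is 1.96 × √(0.5 × 0.5/100) = 9.8 points. It is 9.0 points at 30% and 9.6 at 60%. Every shift in the table is smaller than sampling error, but a larger sample would not remove it.

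**The case against.** The strongest reply is that the document does not state the harmful consequences. Most of this stands, and it limits the point in four ways.

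- **Denominator.** A reader might infer that the plan excludes terminated patients and so reports the rate among those retained. It does not say so. The denominator is undefined, so exclusion is a risk and not a rule.
- **Safety follow-up.** A reader might infer that it ends at termination. The document does not say that either. The event itself is recorded after the injection, contact with all subjects is promised with no exception for terminated ones, and clinic visits are standard of care. The promise is weakened because its review points are tied to sample collections that the schedule does not contain.
- **Delayed complications.** A reader might infer that patients with complications in general are lost, or that the criterion conflicts with listed risks such as "intradiscal infection (discitis), epidural hematoma or abscess". The criterion covers only events identified during the procedure. A complication that appears later does not trigger it, and a procedural criterion need not list delayed risks.
- **Later withdrawal.** A reader might infer that patients cannot withdraw after the procedure. The list does not claim to be exclusive, and the consent pages are not in the text reviewed.

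It is also fair that the upward direction is an assumption, and that counting missing scores as non-response is one choice among several. The lack of a missing-data rule affects every dropout, not only these patients.

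The reply does not remove the criterion itself. Followed as written, it takes patients out of the study because of a safety event, and no other section clearly puts them back.

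**Conclusion.** The concern holds in a limited form. The protocol makes any adverse event during the procedure a termination criterion, does not separate stopping the procedure from leaving the study, and is silent on continued follow-up and on the denominator. Because a stated rule selects patients on a safety outcome, this is more than a missing detail.

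The effect on the responder proportion is probably modest: 0.3 to 1.2 points for one or two terminations and 3 to 6 points for ten, at retained responder rates of 30% to 60%. Those figures assume that terminated patients are dropped from the analysis and would otherwise count as non-responders. The true size cannot be derived from the document. The effect on safety information is a possible gap in the later course of patients whose first event is already recorded; it cannot be put as a number.

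**What to change.** 1. In Study Termination Criteria, separate the two decisions: an adverse event may end the procedure, but it does not by itself end study participation. The clinical decision to stop a procedure is unchanged.
2. State that every patient in whom the injection was started stays in the scheduled questionnaires, examinations and adverse event recording unless consent is withdrawn. Add adverse events to the items collected at the follow-up visits, and tie the committee's review to those visits.
3. In the Data Analysis Plan, report the responder proportions with all such patients in the denominator. Count a missing 2-month NRS as non-response and show the observed-case proportion alongside, so that the reader can see how far the choice matters.

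The cost is small: revised wording, a few more study questionnaires at visits that are already standard of care, and possibly a slightly lower responder rate.
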